10.9.3 Protocol amendment 03 (update from protocol version 3.0 to 4.0)

Overall amendment rationale

This update describes changes made to allow administration of Dose 2 to Group B transplant subjects (Cohort 13 of the BNT162-01 trial) based on an SRC recommendation and for a reduction of the recruitment period.

A comparison of every new sponsor approved protocol version with the next approved version is filed together with the protocol in the TMF.

Detailed description of changes

Minor editorial changes, such as the correction of typing errors, are not specifically listed. See the table for a summary of the reasons for major changes compared to the previous version.

Section	Reason for change
Title page	Change in sponsor's medical representative
1.1 Trial synopsis (Trial rationale), 2.2 Trial rationale	Updates to describe rationale for allowing administration of Dose 2 to Group B transplant subjects.
1.1 Trial synopsis (Trial design, Duration of all trial periods)	Reduction in recruitment period as no subjects from parent trial left for rollover.
1.3 Schedule of activities	A separate SoA table for Group B transplant subjects was added to allow administration of Dose 2. Updates of footnotes in existing tables made to accommodate subjects receiving non-trial SARS-CoV-2 vaccinations.
Throughout	Updating the representative SARS-CoV-2 variants tracked by the WHO, deletion of "SA" from variant B.1.351 (Pango lineage) for clarity of variant names.
2.3.1 Risk assessment	Deletion and updates to reflect more recent information.
3 Objectives and endpoints	Updates to secondary and exploratory endpoints related to Group B transplant subjects due to administration of Dose 2.
6.1 IMPs administered	Addition of dosing regimen for the Group B transplant subjects
6.5 Concomitant therapy	Addition to accommodate subjects receiving non-trial SARS-CoV-2 vaccinations.
7.2 Trial subject discontinuation or withdrawal from the trial	Addition to accommodate subjects receiving non-trial SARS-CoV-2 vaccinations.
8.3.1 Time period and frequency for collecting AE, AESI, and SAE information	Addition to accommodate subjects receiving non-trial SARS-CoV-2 vaccinations.

BioNTech SE	
Confidential	

Section	Reason for change
9.4.5 Other safety analyses	Addition of the Immunology Subgroup of Group B to clinical laboratory parameters and vital signs.
10.3.1 Definition of AE and TEAE	Addition for clarity: AEs with an onset date more than 28 d after the last administration of IMP will be considered as treatment-emergent only if assessed as related to IMP by the investigator
10.3.1.9 Documentation of particular situations	Addition for clarity: Any case of proven COVID-19 disease occurring until the last FU visit should be reported as an SAE/AE

10.10 Data collection and management

The trial documentation must be adequate for the reconstruction of the trial.

10.10.1 Case report forms

CRFs will be completed through use of an electronic data capture (EDC) system. Trial site personnel will receive training and have access to a manual for appropriate CRF completion. The CRFs will be submitted electronically to the sponsor via the system and should be handled in accordance with instructions from the sponsor.

All CRFs should be completed by designated, trained trial site personnel. CRFs should be reviewed, verified, and then electronically signed and dated by the investigator or a designee.

At the end of the trial, the investigator will receive trial subject data for his/her trial site in a readable format that must be kept with the trial records. Acknowledgment of receipt of the trial subject data will be required.

10.10.2 Trial subject reported outcomes

Not applicable.

10.10.3 Data management

The CRO (see the title page) will be responsible for data management of this trial, including quality checking of the data.

Data entered manually will be submitted to the sponsor through use of an EDC system, data extracts, and reports. Trial sites will be responsible for data entry into the EDC system. In the event of discrepant data, the data management service provider will request data clarification from the trial sites, which the trial sites will resolve electronically in the EDC system.

The data management service provider will produce a Trial Data Validation Specification document that describes the quality checking to be performed on the data. CRFs and correction documentation will be maintained in the EDC system's audit trail.

Central laboratory data will be sent directly to the data management service provider.

System backups for data stored by the sponsor and records retention for the trial data will be in accordance with regulatory requirements.

BioNTech SE Confidential Page 89 of 91 Version: 4.0 Date: 20 JAN 2022

10.10.4 Investigator's Site File and the Trial Master File

The principal investigator or deputy is responsible for the filing of all essential documents in an ISF. The sponsor or a delegated CRO is responsible for the timely filing of all essential documents in the Trial Master File. As applicable, these files must be available at monitoring visits and during audits or regulatory inspections.

After trial completion, the principal investigator or deputy must ensure that all source data and documentation related to the trial is recorded, handled, and stored in a way that allows its accurate reporting, interpretation, and verification. The principal investigator or deputy must take measures to prevent accidental or premature destruction of these documents.

The principal investigator or deputy must keep the ISF, the source data/documentation arising from the trial according to the prescribed record retention period in the country and/or according to the hospital policy, but at least until informed by the sponsor that the trial-related records are no longer required.

10.11 Other data

10.11.1 Demographic data

At screening, the following demographic data will be recorded for all trial subjects:

- Age (in years/months)
- Gender (male/female)
- Ethnic group

1.1. Objectives and endpoints

Table 2: Objectives and endpoints

Objectives	Endpoints
Primary	
To determine the safety and tolerability of one or two boosting doses of Comirnaty or one dose of BNT162b2s01 in BNT162- 01 trial subjects, or two boosting doses of Comirnaty in BNT162-04 trial subjects.	 For all Group A and Group B subjects: The proportion of subjects in each treatment group with at least one SAE or the proportion of AESIs occurring up to 26 weeks after the first IMP injection. For Group A and a selected subset of Group B subjects: The frequency of solicited local reactions (pain, tenderness, erythema/redness, induration/swelling) at the injection site recorded up to 7 days after each IMP injection. The frequency of solicited systemic reactions (vomiting, diarrhea, headache, fatigue/tiredness, fever, chills, nausea, new or worsened muscle pain, new or worsening joint pain) recorded up to 7 days after each IMP injection. The proportion of subjects with at least one unsolicited TEAE occurring up to 28 days after IMP injection in each treatment group.

Objectives	Endpoints
Secondary	
To describe changes in SARS-CoV-2 neutralizing antibody titers from baseline to reference and SARS-CoV-2 variant B.1.351.	 For Group A and Group B subjects (except transplant subjects): Antibody titers to recombinant S1 and RBD protein derived from reference and SARS-CoV-2 variant B.1.351** will be assessed at baseline (Day 1) and then Day 8, Weeks 3*, 4, 7*, 12, and 26: Neutralizing antibody titers. Antibody titers (ELISA). SARS-CoV-2 functional cross-neutralization of variant B.1.351** to reference strain.
	 * Group B only ** Group A only For Group B transplant subjects only: Antibody titers to recombinant S1 and RBD protein derived from SARS-CoV-2 will be assessed at baseline (Day 1) and then Day 8, Weeks 4, 12, and 26 post Dose 1, and at Dose 2 (Day 1) and then Day 8, Weeks 4, 12 and, 26 post Dose 2: Neutralizing antibody titers Antibody titers (ELISA)
Exploratory	
To describe B- and T-cell responses to SARS-CoV-2 S and RBD antigens after injection of Comirnaty or BNT162b2s01	 For Group A subjects: Baseline (Day 1) and then at Day 8, and Weeks12 and 26, CMI responses including B cell, CD4 and CD8 T-cell responses to S and RBD antigens of interest. For a selected subset of Group B subjects (except transplant subjects): Baseline (Day 1) and then at Day 8 and Weeks 4, 12, and 26, CMI responses including B cell, CD4 and CD8 T-cell responses to S and RBD antigens of interest. For Group B transplant subjects only: Baseline (Day 1) and then at Day 8, Weeks 4 and 12 post Dose 1 and at Dose 2 (Day 1) and then Day 8, Weeks 4, 12, and 26 post Dose 2 CMI responses

	including B cell, CD4 and CD8 T-cell responses to S and RBD antigens of interest.
To evaluate SARS-CoV-2 viral sequences in trial subjects who become infected (with or without symptoms).	 In subjects who become SARS-CoV-2 infected: SARS-CoV-2 S antigen sequences or whole genome sequencing of interest.
To describe time course changes in antibody titers after IMP injection in this trial in relationship to titer time from the last IMP injection in the BNT162-01 or BNT162-04 trials.	 In a selected subset of subjects in Groups A and B (except transplant subjects): SARS-CoV-2 antibody titers to recombinant S1 assessed at baseline (Day 1), and then at Day 8 and Weeks 12 and 26 to describe any potential time dependency immune responses that may include data from BNT162-01 and BNT162-04 trials for: o Neutralizing antibody titers. o Antibody binding (ELISA titers) to SARS-CoV-2 antigens.
	 For Group B transplant subjects only: SARS-CoV-2 antibody titers to recombinant S1 assessed at baseline (Day 1), and then at Day 8 and Weeks 12 and 26 post Dose 1 and Dose 2 (Day 1) and then Day 8, Weeks 4, 12, and 26 post Dose 2 to describe any potential time dependency immune responses that may include data from BNT162-01trial for: Neutralizing antibody titers. Antibody binding (ELISA titers) to SARS-CoV- 2 antigens.
To evaluate cross- neutralization of vaccine- induced antibodies to emerging SARS-CoV-2 variants.	 In select subjects in Groups A and B: Measure cross-neutralization of other SARS-CoV-2 VOCs (e.g., using pVNT).

Abbreviations: AE = adverse event; AESI = adverse event of special interest; CD = cluster of differentiation; CMI = cell mediated immune response; d = day(s); ELISA = enzyme-linked immunosorbent assay; IMP = investigational medicinal product; pVNT = pseudovirus neutralization test; RBD = receptor binding domain; SAE = serious adverse event; S protein = SARS-CoV-2 spike protein; S1 = the subunit produced after the SARS-CoV-2 S protein is cleaved by host proteases; TEAE = treatment emergent adverse event; VOCs = variants of concern.

1.2. Trial design

Trial design	This is a Phase II, open-label, rollover trial to evaluate the safety and immunogenicity of one or two boost injections of Comirnaty or one dose of BNT162b2s01 in BNT162-01 trial subjects or two boosting doses of Comirnaty in BNT162-04 trial subjects. There will be two groups.
Trial population	Group A: Trial subjects from BNT162-01 who received two injections of 30 µg Comirnaty will be randomized 2:1 to one booster injection (BNT162b2s01:Comirnaty). Day 1 (baseline in this trial) must occur ≥24 weeks after the last Comirnaty injection in the BNT162-01 trial. Note: Transplant subjects from Cohort 13 of the BNT162-01 trial are excluded.
	Group B: Trial subjects in either the trial BNT162-01 or BNT162-04 who did not receive the full two vaccinations of 30 µg Comirnaty will be offered two injections of 30 µg Comirnaty as per the conditional marketing authorization. Day 1 (baseline in this trial) must occur ≥12 weeks after receiving the last BNT162 candidate vaccine in the BNT162- 01 or BNT162-04 trial. Transplant subjects will receive one injection of Comirnaty which will be followed 3 to 7 months afterwards by a second injection of Comirnaty.
	An immunology subset of Group B consenting subjects will participate in more detailed tolerability (reactogenicity) and immunogenicity assessments. Consenting BNT162-01 Cohort 13 transplant recipients will also be included in the immunology subset of Group B.
	A detailed description of the inclusion and exclusion criteria can be found in Section 5.1 and 5.2 of the protocol.
Trial sites	Multiple sites in Germany that participated in the trials BNT162-01 and BNT162-04
Investigational medicinal products	Name: BNT162b2 (Comirnaty [®]) and BNT162b2s01, RNA based vaccines for prevention of COVID-19
	Type: BNT162 RNA-LNP vaccines utilizing modRNA
	For Group A, the vaccine will be administered as booster injection. For Group B, the vaccine will be offered as per the conditional marketing authorization (except for transplant subjects). Consenting transplant subjects will be enrolled into

	Group B immunology subset and will receive one injection of Comirnaty [®] which could be potentially followed 3 to 7 months afterwards by a second injection of Comirnaty [®] . This group will be referred to as Group B transplants. Subjects not eligible during this period due to any medical reason (e.g., breakthrough infection causing investigational medicinal product delay decision from the investigator) will not receive the 4 th dose in this trial. Dose : 30 µg of Comirnaty [®] or BNT162b2s01 Dosing regimen: Group A: One (at Day 1) intramuscular injection with 30 µg of either Comirnaty or BNT162b2s01. Group B: Two (at Day 1 and Day 21) intramuscular injections with 30 µg of Comirnaty, except Group B transplant subjects. Group B transplant subjects: Two intramuscular injections of 30 µg of Comirnaty, with injection 2 administered 3 to 7 months after injection 1 (Day 1). The planned time points for injection of the investigational medicinal product for Groups A and B are provided in the Schedule of Activities in the protocol (Section 1.3)
	Administration route: Intramuscular
Treatment and study duration	In total, the planned trial duration for a subject in this trial is approximately 30 weeks (≤4 weeks of screening and ~26 weeks follow-up).
Planned number of subjects	The maximum number of subjects in Group A will be 90 (including up to 15 HIV-positive subjects) and in Group B will be 459 (including up to15 transplant subjects). A subset of Group B (n=129) will be asked to participate in an immunology subset evaluation.
Randomization and blinding	Subjects in Group A will be randomized in a 2:1 ratio to either BNT162b2s01 or Comirnaty [®] . All subjects in Group B will receive at least one injection of Comirnaty [®] . They will not be randomized. The study is open-label.

1.3. Schedule of visits and procedures

The schedule of visits and procedures can be found in the protocol in Tables 1 (Group A), 2 (immunology subset of Group B, with two injections), 2a (immunology subset of Group B transplant subjects, injection 2), and 3 (Group B without immunologic assessments).

2. Statistical hypotheses

There is no formal statistical hypothesis under test.

3. Interim analyses

No formal interim statistical analysis will be performed. However, preliminary analyses may be performed after completion of Visit 5 for any group (i.e., Group A or Group B).

3.1. Data Monitoring Committee (DMC)

No DMC is planned.

There will be a Safety Review Committee (SRC). For details see protocol Section 10.1.5.

4. Sample size determination

No formal sample size calculations were performed as this rollover trial is based on the trials BNT162-01 and BNT162-04.

5. Analysis sets, protocol deviations and subgroups

5.1. Definition of analysis sets

Screened set (SCR)

The screened set is defined as all subjects who signed informed consent.

Safety set (SAF)

The safety set is defined as all subjects who received at least one dose of investigational medicinal product (IMP).

Safety boost set (SAFB)

The safety boost set is defined as all subjects who received two doses of IMP (first injection (Dose 1) and second injection (Dose 2)).

Note: Group A will be excluded from the SAFB as they receive only a single injection according to protocol.

Immunogenicity set (IMM)

The immunogenicity set is defined as all subjects who received at least one dose of IMP and have at least one post-baseline functional antibody titer (e.g., VNT or an equivalent assay) immunogenicity assessment.

Note: The expression 'have at least one post-baseline functional antibody titer immunogenicity assessment' refers to having either at least one post-baseline neutralizing antibody titer or one post-baseline ELISA titer immunogenicity assessment.

Immunogenicity per-protocol set (IMMPP)

The immunogenicity per-protocol set is defined as all subjects included in the immunogenicity set that have no major protocol deviations as determined by the clinician and who received two doses of IMP (first injection (Dose 1) (for Group A and B) and second injection (Dose 2) (only for Group B)).

Note: Subjects with any major protocol deviation thought to interfere with either the mechanism of action or immunogenicity test measurements will be excluded from IMMPP set.

Note: The definitions of all analysis sets apply within the BNT162-14 trial. In all analysis sets, subjects will be assigned to the treatment groups (i.e., vaccine type) according to the actual treatment they received ("as treated"). The condition of receiving two doses of IMP will not apply to Group A.

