9.3 Analysis sets

The following analyses sets are defined:

Analysis set	Description
Screened Set	All subjects who signed informed consent.
Safety Set	All subjects who received at least one dose of IMP.
Immunogenicity Set (IMM)	All subjects who received at least one dose of IMP and have at least one post- baseline functional antibody titer immunogenicity assessment.

Analysis set	Description
Immunogenicity Per- Protocol set (IMMPP)	All subjects included in the IMM set that have no major protocol deviations as determined by the clinician.

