9.4.3 Secondary endpoints

The secondary endpoints are defined in Section 3.

All secondary immunogenicity analyses will be performed first with the IMM population (see Section 9.3) as this is an exploratory hypothesis-generating trial. However, the Immunogenicity Per Protocol set (IMMPP) population will also be analyzed.

The scheduled time points for assessment are given in the SoA (see Section 1.3).

The binary secondary endpoints will be summarized by group presenting absolute and relative frequencies (n and %) of subjects in each category for each assessment. The continuous secondary endpoints will be summarized by group using summary statistics.

For each subject and each time point, antibody titers will be defined based on the calculated geometric mean of antibody titers assessed in duplicate. Additionally, GMT with 95% CI will be presented.

Change in antibody titers to recombinant S1 and RBD protein derived from reference and B.1.351 strains will be assessed from baseline to time points as identified in the endpoints (see Section 3) and SoA (see Section 1.3). In addition to analysis of changes in

BioNTech SE	Clinical Trial Protocol	Page 59 of 91
Confidential	BNT162 14	Version: 4.0
Comidentia	DINT 102-14	Date: 20 JAN 2022

neutralizing antibody and binding antibody titers, functional cross-neutralization of vaccineinduced antibodies to B.1.351 in relationship to reference strain will be analyzed at time points identified in the secondary endpoints.

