Important Case Report Form (CRF) data and all relevant generated and transformed variables together with the original data items will be listed. Separate listings will be provided for Group A and B and immunology subset of Group B. Listings will be sorted first by vaccine (for Group A), subgroup (HIV-positive subjects for Group A, transplant subjects for Group B or immunology subset of Group B), site ID and by subject number and finally, if applicable, by visit number and/or a relevant date (e.g., date of onset of AE).

Programming

SAS[®] (version 9.4 or higher) programming will be performed according to Staburo GmbH standards as defined in SOP001_PROGRAMMING [1] and related work instructions. Special attention will be paid to planning and performance of quality control measures as documented in the quality control plan for the analysis of this study (see also SOP002_PROGRAM_QC [2]).

Analysis sets

The SCR will be used for disposition. The SAF will be used for analysis of safety and adverse events data. Some analyses of the adverse events will be repeated for Group B using the SAFB if the SAF and the SAFB sets differ. The IMM will be used for the analysis of immunogenicity data. The immunogenicity analyses may be repeated using the IMMPP if the two analysis sets differ significantly. This will be decided at the data review meeting.

Data of subjects who failed to complete all visits of the trial (dropout or withdrawal) will be reported as far as their data is available.

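### The SAP adds an undeclared two-dose condition to the per-protocol immunogenicity set and makes its analysis optional, so compliant one-dose transplant subjects are missing from the supportive post-Dose-1 results

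*SAP*

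**What the plan says.** **Who is in the set.** Protocol 9.3 defines the IMMPP as "All subjects included in the IMM set that have no major protocol deviations as determined by the clinician". It sets no number of doses. SAP 5.1 keeps the deviation rule and adds "and who received two doses of IMP (first injection (Dose 1) (for Group A and B") plus a second injection for Group B. The closing note of that section waives the condition for one group: "The condition of receiving two doses of IMP will not apply to Group A". Transplant subjects have no such waiver.

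**Whether the set is analysed.** Protocol 9.4.3 analyses the IMM first and then states: "However, the Immunogenicity Per Protocol set (IMMPP) population will also be analyzed". SAP 6.1.1 reads: "The immunogenicity analyses may be repeated using the IMMPP if the two analysis sets differ significantly". It leaves the decision to the data review meeting. SAP 6.5 likewise treats the IMMPP as a possible addition.

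**Whether transplant subjects always receive Dose 2.** SAP 1.2 describes one injection "which could be potentially followed 3 to 7 months afterwards by a second injection" and says that subjects medically ineligible in that window get no fourth dose in this trial. The footnotes to protocol Table 2 tie the second injection to a recommendation of the safety review committee (SRC) and to new consent at Visit 6 or 7. Protocol 1.1 and 4.1, and the trial population entry in SAP 1.2, instead present it as something that will follow.

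**What is declared.** SAP section 1 says that changes from the protocol are documented in Appendix 7.1. That appendix has one entry, on adverse event grades.

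**The concern.** A per-protocol set should keep subjects who did what the protocol asked. For the titers after Dose 1, that means receiving Dose 1 and having no major deviation. The SAP also requires an injection given 3 to 7 months later. Whether a subject's Day 8 or Week 4 titer counts then depends on later infection, later health, later willingness or a committee recommendation.

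The transplant post-Dose-1 series is a secondary endpoint in its own right, and the group is small, so a few exclusions change its summaries visibly. The IMMPP is also the planned check on the IMM result. The SAP alters its membership and makes its production discretionary under a criterion that it does not define. A reader who relies on Appendix 7.1 would notice neither change.

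**Working it through.** The plan has no hypothesis and no sample size calculation, so there is no stated figure to reproduce. The check is a comparison of text, followed by an illustration of size.

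**Step 1: membership.**

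| Subject | Protocol 9.3 | SAP 5.1 |
|---|---|---|
| Group A, one dose, no major deviation | in | in (waiver) |
| Group B, two doses, no major deviation | in | in |
| Group B transplant, one dose, no major deviation | in | out, at all time points |
| Other Group B, one dose, no major deviation | in | out, at all time points |

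**Step 2: can the third row occur?** Yes. The SRC may not recommend Dose 2, the subject may not consent at Visit 6 or 7 (protocol Table 2 footnotes), or the subject may be medically ineligible (SAP 1.2). The list of major deviations in SAP 5.2 does not name a missed second injection. Its nearest items are a wrong vaccine or dose and non-compliance, and a subject covered by one of these routes fits neither clearly. The fourth row is less certain. Protocol 7.1.1 allows Group B subjects to stop the vaccine and asks them to complete the remaining assessments, but the medical review might class some of these cases as major deviations.

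**Step 3: timing.** Transplant titers after Dose 1 are due at Day 8 and Weeks 4, 12 and 26 (protocol section 3). With the SAP's conversion of 30.25 days per month, the earliest Dose 2 falls 3 × 30.25 = 90.75 days after injection 1. The Week 4 visit (Day 29) is nominally 28 days after injection 1, so 90.75 − 28 = 62.75 days earlier. The Week 12 visit (Day 85) is nominally 84 days after, also before that point. These values are fixed before the event that decides whether they count.

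Week 26 is the most exposed. Protocol Table 2 requires Visit 7 to be skipped when consent is taken at Visit 6. Week 26 titers therefore come mainly from subjects who consented at Visit 7 and from those who never received Dose 2. The SAP's IMMPP removes the second kind.

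**Step 4: size.** Inputs are 15 transplant subjects at most, 129 in the immunology subset and 459 at most in Group B (protocol 4.1).

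- Ceiling: 15/459 = 3.3% of Group B; 15/129 = 11.6% of the immunology subset; up to all of the transplant stratum.
- Precision: half-width of the 95% CI for the mean log titer, in SD units, is t(0.975, n − 1)/√n. The SD is held constant.

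| One-dose subjects (assumed) | Left in IMMPP | Removed | Half-width (SD) |
|---|---|---|---|
| 0 | 15 | 0% | 0.554 |
| 3 | 12 | 20% | 0.635 |
| 5 | 10 | 33% | 0.715 |
| 10 | 5 | 67% | 1.242 |

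Three one-dose subjects widen the interval by 0.635/0.554 − 1 = 15%, and five by 0.715/0.554 − 1 = 29%. This applies to IMMPP tables only.

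**Step 5: the optional analysis.** The protocol's commitment is unconditional. The SAP's trigger is a significant difference between the sets, but no threshold is given and SAP 6.1 rules out formal testing. The trigger cannot be applied reproducibly.

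**The case against.** The main objection is that the IMMPP is only supportive. The IMM needs one dose and is the set for all secondary immunogenicity analyses, so one-dose transplant subjects keep their post-Dose-1 titers in every main table. This stands. A reader might infer that these subjects are dropped from the Dose 1 results altogether; they are not. Nor does the optional wording exclude anyone: it decides only whether IMMPP tables exist.

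A reader might also infer that the selection favours better responders. The documents do not show this. Protocol 2.2 justifies a fourth dose partly by its effect in low responders and non-responders, so weak responders may be keener to take it. A subject who misses it after a breakthrough infection need not have a low titer. The direction is unknown.

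A third tempting inference is that the sponsor could omit the IMMPP analysis after seeing unfavourable results. The SAP's trigger is a difference between the sets, not between results. SAP 5.2 places identification of major deviations before the database snapshot, and SAP 6.2 lists subjects excluded from the IMMPP with reasons. The trial is open-label and preliminary analyses are allowed after Visit 5, so some data may be known by then, but nothing in the text makes the choice depend on results.

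Finally, some passages present the transplant regimen as two injections, and a per-protocol set requiring both would fit them. That is a fair reading of those passages. It conflicts with the ones that make the second injection conditional, and it does not justify removing titers taken before that injection was due.

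**Conclusion.** The point holds in limited form. The SAP departs from the protocol twice, in who belongs to the IMMPP and in whether it is analysed, and declares neither departure where it says it will. Because of the first, transplant subjects who complied but had no Dose 2 for a reason that the documents allow are missing from the IMMPP at all time points. The supportive post-Dose-1 results are then conditioned on later events.

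The effect is bounded. It concerns at most 15 transplant subjects, and an unknown number of other Group B subjects whose missed second injection is not classed as a major deviation. The IMM results are unaffected by this condition. The losses of 20% and 33% rest on assumed counts of three and five one-dose subjects; if all 15 received Dose 2, no transplant subject is lost to it. The change is worth making because it is cheap and because, in a descriptive trial, the analysis set determines what is reported.

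**What to change.** 1. In SAP 5.1, define the IMMPP by dose series. For the post-Dose-1 series, use the protocol 9.3 definition ("that have no major protocol deviations as determined by the clinician") with no dose count. This series covers all scheduled visits in protocol Table 2 for transplant subjects and the visits before Dose 2 for other Group B subjects. Tying it to the visit table also handles subjects who have no Dose 2 date.
2. Require Dose 2 only for the post-Dose-2 series: Table 2a visits for transplant subjects, and visits after injection 2 for other Group B subjects.
3. In SAP 6.1.1 and 6.5, replace the optional repeat with a commitment that the immunogenicity analyses will be repeated in the IMMPP, as in protocol 9.4.3.
4. List any remaining difference from the protocol in Appendix 7.1.
5. Reconcile the passages that present the transplant second injection as following (protocol 1.1 and 4.1, SAP 1.2 trial population) with those that make it conditional (protocol Table 2 footnotes, SAP 1.2 investigational products). Which is correct is for the sponsor to settle.

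The cost is SAP wording and one more run of the existing titer programs. No new data are needed.
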